11.5 Future Use of Stored Samples

Any remnant (leftover) blood samples collected for the anti-CHIKV SNA analysis will be retained for future testing. Specimens will be identified by sample numbers/codes, thereby maintaining blinding while in storage. Subjects will be asked to consent to the future use of these samples as part of the informed consent process.

Samples may be retained for at least two years after the last approval of a marketing application in an ICH region and until there are no pending or contemplated marketing applications in an ICH region or until at least two years have elapsed since the formal discontinuation of clinical development.

12 ADMINISTRATIVE AND LEGAL REQUIREMENTS

12.1 Sponsorship

This clinical study is sponsored by Emergent Travel Health Inc. [REDACTED] The manufacturer of PXVX0317 is Emergent BioSolutions Inc.

12.2 Protocol Amendments

Protocol amendments will only be made by the Sponsor. In general, any change to the protocol must be made in the form of a formal amendment to the protocol and must be approved in writing by the Principal Investigator, the Sponsor, and the IRB prior to implementation. The Investigator must receive written IRB approval for all protocol amendments prior to implementing protocol amendments at the study site. The Investigator must send a copy of any IRB correspondence and all approval/disapproval letters from the IRB to the Sponsor.

A protocol change intended to eliminate an apparent immediate hazard to participants will be implemented immediately, followed by IRB notification within five working days.

The Sponsor will submit protocol amendments to the applicable regulatory authority(ies).

12.3 Clinical Study Registration

For purposes of clinical study registration including reporting to ClinicalTrials.gov, the Sponsor is the responsible party and will provide information regarding this study in accordance with applicable regulations.

12.4 Publication Policy

Following the completion of the study, the data may be considered for reporting at a scientific meeting or for publication in a scientific journal. In these cases, Sponsor will be responsible for these activities and may work with the Investigator(s) to determine how the manuscript is written and edited, the number and order of authors, the publication to which it will be submitted and other related issues. Sponsor has final approval authority over all such issues.

Any proposed publication will be subject to review conditions and timelines agreed between Sponsor and the site Investigator and detailed in the agreements with these parties prior to the start of the study. The Sponsor will also post the results of the clinical study on ClinicalTrial.gov in a period no greater than 12 months from the completion of the study, defined as the time the final participant was examined or received an intervention for purposes of final collection of data for the primary outcome.

Data are the property of the Sponsor and cannot be published without prior authorization from the Sponsor, but data and publication thereof will not be unduly withheld.

All publication rights are delineated in the Clinical Trial Agreement.

12.5 Terminating the Study

The Sponsor and/or the Principal Investigator may elect to terminate the study early as defined by the clinical study agreement. The Sponsor reserves the right to terminate the study at any time for clinical or administrative reasons. Any decision to voluntarily suspend or terminate a clinical study will be carefully reviewed and fully justified. The Sponsor will notify the FDA and the IRB of any suspension or termination and provide the justification. The Principal Investigator must notify the IRB in writing of the study's completion or early termination. The Sponsor must receive a copy of the notification letter from the IRB indicating receipt of the completion or early termination letter.

12.6 Terminating the Study at an Individual Site

A study site may be terminated from the study at the discretion of the Principal Investigator, Sponsor, or IRB. Sponsor may decide to replace a terminated site.

APPENDIX I SUMMARY OF BLOODWORK

Study Visit	Screening		Day 1		Day 8		Day 15		Day 22		Day 57	
Procedure	Blood Draw		Blood Draw including PBMCs		Blood Draw including PBMCs		Blood Draw including PBMCs		Blood Draw including PBMCs and Plasmapheresis		Blood Draw including PBMCs and Plasmapheresis	
Assay	ELISA ¹ (IgG)		ELISA ² (IgM and IgG)		ELISA ² (IgM and IgG)							
	HBsAg, anti-HCV, HIV 1/2 Ag/Ab (local lab)		CHIKV-luc		CHIKV-luc		CHIKV-luc		CHIKV-luc		CHIKV-luc	
			ELISpot and flow cytometry		ELISpot and flow cytometry							
Tubes	SST	CPT	SST	CPT	SST	CPT	SST	CPT	SST	CPT	SST	CPT
	3	0	2	8	2	8	2	8	10	8	10	8
Volume (mL, max)	15	0	10	64	10	64	10	64	50	64	50	64
Total Volume Serum (mL, max)	15		74		74		74		114		114	
Total Volume Plasma (mL)	0		0		0		0		~690-880 mL per subject (weight based)		~690-880 mL per subject (weight based)	

SST, serum-separating tube; CPT, cell preparation tubes; ELISA, enzyme-linked immunosorbent assay; PBMC, peripheral blood mononuclear cell; ELISpot, enzyme-linked immune absorbent spot; HBsAg, Hepatitis B surface antigen; anti-HCV, Hepatitis C virus antibody; HIV1/2 Ag/Ab, human immunodeficiency virus antigen/antibody.

¹ Screening will be performed by PPD using the EUROIMMUN Anti-CHIKV IgG ELISA kit.

² Study sample testing will be performed by Emergent using InBios Anti-CHIKV IgG and IgM ELISA kits.

APPENDIX II GRADING SCALE

EVENT	MILD (Grade 1)	MODERATE (Grade 2)	SEVERE (Grade 3)	POTENTIALLY LIFE THREATENING (Grade 4)
Fever	$\geq 100.4-101.1^{\circ}\text{F}$ ($\geq 38.0-38.4^{\circ}\text{C}$)	$\geq 101.2-102^{\circ}\text{F}$ ($\geq 38.5-39^{\circ}\text{C}$)	$\geq 102.1^{\circ}\text{F}-104^{\circ}\text{F}$ ($\geq 39^{\circ}\text{C}-40^{\circ}\text{C}$)	$>104^{\circ}\text{F}$ ($>40^{\circ}\text{C}$)
Headache	No interference with activity	Some interference with activity, may require repeated use of non-narcotic pain reliever for more than 24 hours	Significant, prevents daily activity, any use of narcotic pain reliever	ER visit or hospitalization
Fatigue	No interference with activity	Some interference with activity	Significant, prevents daily activity	ER visit or hospitalization
Myalgia	No interference with activity	Some interference with activity	Significant, prevents daily activity	ER visit or hospitalization
Nausea	No interference with activity	Some interference with activity	Significant, prevents daily activity	ER visit or hospitalization
Chills	No interference with activity	Some interference with activity not requiring medical intervention	Prevents daily activity and requires medical intervention	ER visit or hospitalization
Arthralgia	No interference with activity	Some interference with activity not requiring medical intervention	Prevents daily activity and requires medical intervention	ER visit or hospitalization
Injection site pain	Does not interfere with activity	Repeated use of non-narcotic pain reliever > 24 hours or interferes with activity	Use of any narcotic pain reliever or prevents daily activity	ER visit or hospitalization
Injection site erythema/redness	25-50 mm*	>50 mm-100 mm*	>100 mm*	Necrosis or exfoliative dermatitis
Injection site induration/swelling	25-50 mm* and does not interfere with activity	>50 mm-100 mm* or interferes with activity	>100 mm* or prevents daily activity	Necrosis

*Revised by Sponsor

9.3.5	Adverse Events Leading to Study Discontinuation from Day 1 to Day 183 End of Study Visit.....	29
9.4	Clinical Laboratory Tests.....	29
9.4.1	Pregnancy Testing.....	29
9.4.2	Viral Serology Testing at Screening	29
9.5	Vital Signs, Physical Findings and Other Variables Related to Safety.....	29
9.5.1	Vital Signs.....	29
9.5.2	Physical Examinations	29
10	DATA MONITORING AND INTERIM ANALYSIS.....	30
10.1	Safety Monitoring Committee	30
10.2	Interim Analysis	30
11	REFERENCES.....	31

Appendices

APPENDIX I	LIST OF TABLES, FIGURES AND LISTINGS.....	32
APPENDIX II	TOXICITY GRADING SCALE.....	35
APPENDIX III	STANDARD MEDDRA QUERY FOR ARTHRITIS	36

List of Figures

Figure 1:	EBSI-CV-317-010 Schematic Diagram of Study Design.....	10
Figure 2:	Schedule of Events.....	12

List of Abbreviations and Definition of Terms

AE	Adverse Event
AESI	Adverse Event of Special Interest
ATC	Anatomic Therapeutic Chemical classification
CI	Confidence Interval
CHIKV	Chikungunya Virus
CSR	Clinical Study Report
CTMS	Clinical Trial Management System
eCRF	Electronic Case Report Form
EDC	Electronic Data Capture
ELISA	Enzyme-linked Immunosorbent Assay
ELISpot	Enzyme-linked Immunosorbent Spot
EOS	End of Study Visit
FDA	Food and Drug Administration
GMFI	Geometric Mean Fold Increase
GMT	Geometric Mean Titer
HBsAg	Hepatitis B Surface Antigen
HCV	Hepatitis C Virus
HIV	Human Immunodeficiency Virus
ICF	Informed Consent Form
ICH	International Conference on Harmonisation
IgG	Immunoglobulin G
IgM	Immunoglobulin M
IM	Intramuscular
IP	Investigational Product
LLOQ	Lower Limit of Quantitation
luc	Luciferase Assay
MAAE	Medically Attended Adverse Event
MedDRA	Medical Dictionary for Regulatory Activities
mITT	Modified Intent-to-Treat
mL	milliliter(s)
mm	millimeter(s)
NT ₈₀	80% Neutralizing Titer
PBMC	Peripheral Blood Mononuclear Cell
PT	Preferred Term
PXVX0317	Vaccine Investigational Product
SAE	Serious Adverse Event
SAP	Statistical Analysis Plan
SD	Standard Deviation
SDTM	Standard Data Tabulation Model

SMC	Safety Monitoring Committee
SMQ	Standard MedDRA Query
SNA	Serum Neutralizing Antibody
SOC	System Organ Class
SR	Seroresponse Rate
TLF	Tables, Listings and Figures
US	United States
VLP	Virus-like Particle
WHO	World Health Organization

1 INTRODUCTION

This Statistical Analysis Plan (SAP) is based on Protocol EBSI-CV-317-010, “A Phase 2 Open-Label Study to Assess the Safety and Immunogenicity of PXVX0317 (Chikungunya Virus-Like Particle Vaccine [CHIKV VLP], alum-adjuvanted) (Version 4.0 07-DEC-2021). This document specifies details of the definitions of the derived variables, analysis methods, assumptions, and data handling conventions. The document is accompanied by mock-up tables, listings, and figures (TLF shells). Some further details on the calculation of derived variables will be provided as programmer’s notes in the TLF shells. The TLF shells serve only as a guide for programming the final TLF. They are working documents and can be updated as needed.

2 PROTOCOL SUMMARY

2.1 Study Objectives

2.1.1 Primary Objectives

- To assess the induction of CHIKV neutralizing antibody responses following a single adjuvant dose of PXVX0317 (40 µg CHIKV VLP adjuvanted with 300 µg Alhydrogel) as measured 21 days (Day 22) after vaccination.
- To assess the induction of CHIKV neutralizing antibody responses following a single adjuvant dose of PXVX0317 as measured 7 days (Day 8), 14 days (Day 15), and 56 days (Day 57) after vaccination.

2.1.2 Secondary Objective

- To assess the safety of a single dose of PXVX0317 in healthy adults.

2.1.3 Exploratory Objectives

[figure not shown]
- To obtain plasma and sera at Days 22 and 57 from subjects immunized with a single dose of PXVX0317 to support nonclinical studies.
- To characterize the kinetics of CHIKV IgM, IgG, and neutralizing responses following a single dose of PXVX0317 as measured 7, 14, 21, and 56 days (Days 8, 15, 22, and 57) after vaccination.
- To characterize T and B-cell responses following a single dose of PXVX0317 with collections of peripheral blood mononuclear cells (PBMCs) 7, 14, 21, and 56 days (Days 8, 15, 22, and 57) after vaccination.

2.2 Study Design and Conduct

Study EBSI-CV-317-010 is an open-label, single arm Phase 2 study in healthy adults 18 to 45 years of age. The sample size target is 25 subjects recruited at a single center in the U.S. The study has a screening period of up to 30 days, a treatment and observation period from

Day 1 to Day 22, and a follow-up period through Day 183 (see Figure 1). Subjects receive CHIKV VLP at a dose of 40 µg in combination with 300 µg Alhydrogel via intramuscular (IM) injection in the deltoid muscle on Day 1, have follow-up visits on Day 8, Day 15, and Day 22, with an additional plasmapheresis procedure and collection of serum on Day 22. A phone call follow-up visit occurs on Day 29, followed by a second plasmapheresis procedure and collection of serum at Day 57. Final phone call follow-up visits to assess safety and concomitant medications occur on Day 64 and Day 183, the End of Study (EOS).

Figure 1: EBSI-CV-317-010 Schematic Diagram of Study Design

Note: Days 29, 64, and 183 are phone calls.

Refer to Figure 2, Schedule of Events, for a table of assessments at each visit. The per subject estimated total study duration is 7 months. Screening assessments include informed consent, review of eligibility criteria, medical history, prior and concomitant medications, demography, physical examination including height and weight for body mass index calculation, vital signs, urine pregnancy test for female subjects of child-bearing potential, viral markers for hepatitis B surface antigen (HBsAg), hepatitis C (HCV) and human immune deficiency virus 1 and 2 (HIV-1/HIV-2), and CHIKV IgG antibody enzyme-linked immunosorbent assay (ELISA). Detectable CHIKV IgG antibody by ELISA at screening is an exclusion criterion.

Prior to investigational product (IP) administration on Day 1 (baseline), eligibility, medical history and concomitant medications are reviewed, a negative urine pregnancy test result is required for female subjects of child-bearing potential, and baseline samples are drawn for CHIKV serum neutralizing antibodies (SNA), PBMCs, and CHIKV specific IgG and IgM antibody levels. A directed physical examination is performed if indicated at any scheduled visit. Vital signs including blood pressure, heart rate, respiratory rate and temperature are taken on Day 1 before and after IP administration. Following vaccination, subjects are observed in clinic for 30-60 minutes.

Local and systemic solicited adverse events (AEs) occurring within 7 days after injection are recorded by the subject using a memory aid (i.e., paper diary). Subjects are specifically asked to record local injection site events (pain, redness, swelling) and systemic events (oral

temperature $\geq 100.4^{\circ}\text{F}$, chills, fatigue, headache, myalgia, joint pain, and nausea) each day for the collection period. Memory aids are reviewed at the Day 8 visit, and the Principal Investigator assesses AE severity and causality. Unsolicited AEs are monitored from Day 1 through Day 29; serious adverse events (SAEs) and adverse events of special interest (AESI; see Section 6.3 for definition) are monitored for the duration of the study. Any AEs occurring within 30 minutes of the plasmapheresis procedures at Days 22 and 57 are collected as well. Information on all concomitant medications used through Day 29 is recorded; after Day 29, only information on concomitant medications used for the treatment of an SAE or AESI is recorded. No safety laboratory samples are collected as part of the study.

After screening, blood is collected for immunogenicity assessments at Days 1 (before the vaccination), 8, 15, 22, and 57. SNA responses to CHIKV VLP are determined by a luciferase based CHIKV neutralization assay (CHIKV-luc). Titers are expressed as the reciprocal of the serum dilution achieving 80% neutralization (NT₈₀). CHIKV ELISA IgG and IgM titers are defined per commercial test kits (InBios) utilizing a sandwich method with horseradish peroxidase plus 3,3',5,5'-tetramethylbenzidine optical density quantitation. The provisional threshold for seroresponse is CHIKV SNA titer ≥ 40 , should a definitive seroresponse threshold not be determined prior to final analysis; subjects meeting other CHIKV SNA titer thresholds ($\geq 15, 40, 60, 80, 100, 160, 640$, and 4-fold rise over baseline) will be summarized.

There is no Safety Monitoring Committee (SMC) for this study.

Figure 2: Schedule of Events

Visit	Screen (Visit 1)	Day 1 (Visit 2)	Day 8 (Visit 3)	Day 15 (Visit 4)	Day 22 (Visit 5)	Day 29 (Visit 6) (phone call)	Day 57 (Visit 7)	Day 64 (Visit 8) (phone call)	Day 183 (Visit 9) (phone call)	EOS Visit	Early D/C
Window	-30 days	0	+3d	±2d	+5d	-1/+5d	+5d	-1/+5d	-14/+7d	n/a	
Informed Consent	X										
Medical History	X	X ⁵									
Demographics	X										
Physical Exam ¹	X										
HBsAg, anti-HCV ¹² , HIV 1/2 Ag/Ab ¹³	X										
CHIKV IgG Antibody ELISA (kit at site) ¹³	X										
Inclusion/Exclusion Criteria	X	X ⁵			X ⁸		X ⁸				
Vital Signs	X	X ³									
Pregnancy Test ⁴	X	X ⁵			X		X				X ²
Study Vaccine Administration		X									
Acute Observation (30 min) ⁹		X			X		X				
Issue Memory Aid, Thermometer & Ruler		X									
Review Memory Aid			X								X ⁶
Adverse Event Evaluation ¹⁰		X	X	X	X ⁷	X	X ^{7,10}	X ¹⁰	X ¹⁰		X ¹⁰
Prior/Con Med Evaluation ¹¹	X	X ³	X	X	X	X	X	X	X		X
Anti-CHIKV Neutralization (Serum) ¹³		X ⁵	X	X	X		X				X

PBMC Collection (B+T cells) ¹³		X ⁵	X	X	X		X			X
Blood for ELISA (IgM/IgG) ¹³		X ⁵	X	X	X		X			X
Plasmapheresis and Serum Collection (for nonclinical					X		X			

D/C, discontinuation; n/a, not applicable; HBsAg, Hepatitis B surface antigen; anti-HCV, Hepatitis C virus antibody; HIV1/2 Ag/Ab, human immunodeficiency virus antigen/antibody; CHIKV, chikungunya virus; Con Med, concomitant medication; ELISA, enzyme-linked immunosorbent assay; min, minute; PBMC, peripheral blood mononuclear cells; EOS, End of Study.

¹Complete physical examination at Screening Visit only; Directed physical exam, if indicated by updated medical history at Visit 2 and as needed in subsequent visits.

²Only if before Day 57.

³To be taken prior and after Study Vaccine administration.

⁴Urine pregnancy test at Screening, prior to Study Vaccine administration and prior to plasmapheresis.

⁵Done pre-vaccination.

⁶If the visit occurs within seven days after Study Vaccine administration.

⁷Adverse events occurring 30 mins post plasmapheresis at Day 22 and 57 will be collected.

⁸Confirmation of continued eligibility prior to plasmapheresis procedure.

⁹Subjects will be monitored by study staff for signs of an acute adverse reaction for 30 mins after injection but no more than 60 mins after injection.

¹⁰Solicited AEs from Days 1 to 7, Unsolicited AEs to Day 29; After Day 29, collect SAE and AESI only.

¹¹After Day 29, concomitant medications are collected only for SAEs and AESI.

¹²If anti-HCV positive HCV RNA testing will be performed.

¹³Table summarizing bloodwork by procedure, assay, collection tubes, and the total volume of plasma and/or serum by visit is provided in protocol Appendix I.

2.3 Randomization and Blinding

2.3.1 Method of Randomization

Study EBSI-CV-317-010 is not a randomized study.

2.3.2 Randomization Errors

Not applicable.

2.3.3 Blinding and Unblinding

Study EBSI-CV-317-010 is not a blinded study.

3 STUDY ENDPOINTS

3.1 Primary Immunogenicity Endpoints

- CHIKV SNA seroresponse rate and associated 95% confidence interval (CI) at Day 22.
- CHIKV SNA geometric mean titer (GMT) and associated 95% CI at Day 22.
- CHIKV SNA seroresponse rate and CHIKV SNA GMTs with associated 95% CIs at Days 8, 15, and 57.
- CHIKV ELISA IgG and IgM GMTs with associated 95% CIs at Days 8, 15, 22, and 57.
- Geometric mean fold increase (GMFI) in anti-CHIK SNA titer from Day 1 to Days Days 8, 15, 22, and 57.
- GMFI in CHIKV ELISA IgG and IgM titer from Day 1 to Days Days 8, 15, 22, and 57.
- Numbers and percentages of subjects with an CHIKV SNA titer ≥ 15 , 40, 60, 80, 100, 160, 640, and 4-fold rise over baseline thresholds.

Each endpoint is summarized overall and by sex and by race group (white and non-white).

3.2 Safety Endpoints

- Incidence of solicited AEs through Day 8.
- Incidence of unsolicited AEs through Day 29.
- Incidence of AESIs and SAEs through Day 183/EOS.
- Incidence of AEs within 30 minutes of plasmapheresis on Days 22 and 57.

Each endpoint is summarized overall and by sex and by race group (white and non-white).

3.3 Exploratory Immunogenicity Endpoints

- Kinetics of CHIKV immune responses (via SNA and ELISA; i.e., primary endpoints) over time.

- T and B cell responses from PBMC samples, including enzyme-linked immune absorbent spot (ELISpot) and flow cytometry results, at Days 1, 8, 15, 22, and 57.

4 POWER AND SAMPLE SIZE CONSIDERATIONS

The sample size is based on practical, rather than statistical, considerations. Twenty-five subjects will provide adequate plasma and serum for future non-clinical purposes.

5 DATA CONSIDERATIONS

5.1 Protocol Deviations

A deviation occurs when site personnel or a subject does not adhere to the protocol's stipulated requirements, whether inadvertently or planned. All identified protocol deviations are documented (entered by the monitor in the Clinical Trial Management System [CTMS]) and classified by category and type (important/not important). In addition, programmatic checks for protocol deviations are run by the Sponsor. Programmatically identified protocol deviations are also entered to the CTMS and classified by category and type (important/not important).

5.1.1 Important Deviations

Important protocol deviations are defined by ICH E3 as those "that might significantly affect the completeness, accuracy, and/or reliability of the study data or that might significantly affect a subject's rights, safety, or well-being" (2). Examples of important protocol deviations include:

- Subjects who were enrolled but did not meet study eligibility criteria.
- Subjects who received a prohibited prior or concomitant medication or vaccine.
- Subjects who previously received an investigational CHIKV vaccine/product, including subjects that are vaccinated more than once in the EBSI-CV-317-010 study.
- Other deviations from key study procedures such as subject noncompliance with assessment of primary outcome measures (e.g., missing samples, significantly out of window assessments).

5.1.2 Reporting of Protocol Deviations

All protocol deviations will be contained in the Study Data Tabulation Model (SDTM) datasets. Protocol deviations assessed as important are tabulated and listed by subject for the safety population (see Section 7.2).

5.2 Analysis Populations

Analysis is based on the following study populations:

Enrolled Population: All screened subjects who sign informed consent, are entered in the electronic data collection (EDC) database, and meet all eligibility criteria.

Exposed Population: All subjects who receive IP.

Safety Population: All subjects in the exposed population who provide safety assessment data. This generally includes any subject who was not lost to follow-up at Day 1 (baseline), as they will be at risk for reporting an SAE. All safety analyses use the safety population.

Modified Intent-to-Treat (mITT) Population: All subjects who are vaccinated and have at least one post-injection CHIKV SNA NT₈₀ result.

5.3 Analysis Groups

Tables are displayed with a single column for this open-label, single arm study.

5.4 Analysis Time Points

For immunogenicity analyses, CHIKV SNA samples are collected at Day 1 (baseline), Day 8 (+3 days), Day 15 (± 2 days), Day 22 (+5 day) and Day 57 (+5 days). For all time points, all available data (including out of window data) are included in the summaries according to the analysis set defined for a subject's inclusion.

Data collected at the early discontinuation visit or at unscheduled visits are not presented in the by-visit summary analyses but are included in data listings by subject.

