5.2.10 Early Discontinuation/Withdrawal Visit

All subjects who discontinue study participation before the Day 57 visit will be requested to undergo an Early Discontinuation/Withdrawal Visit. The following will be conducted:

- Review AEs, AESI and SAEs
- Review concomitant medications associated with new or ongoing AEs and any AESIs or SAEs
- Blood collection for anti-CHIKV SNA, ELISA, PBMC
- For women of CBP: urine pregnancy test

If the visit occurs within 7 days after study vaccine administration, the following will also be conducted:

- a. Review of the memory aid
- b. AE (solicited) evaluation

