5.2.11 Unscheduled Visits

Any study procedure, excluding vaccination or plasmapheresis, may be conducted at an Unscheduled Visit as needed and recorded on the Unscheduled Visit eCRF. Examples include repeat specimen collection and additional safety follow-up for an AE/SAE/AESI.

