5.6 Multiple Records in an Analysis Window

If more than one sample is collected for CHIKV SNA NT₈₀ assessment for a given time point, the sample closest to the nominal time point is used for analysis.

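### SAP 5.4 excludes in-window immunogenicity samples from unscheduled and early-discontinuation visits, so a valid Day 22 draw can be treated as missing

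*SAP*

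**What the plan says.** SAP 5.4 sets two rules for the immunogenicity tables.

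- Scheduled visits: "For all time points, all available data (including out of window data) are included in the summaries". No outer limit is given.
- Other visits: "Data collected at the early discontinuation visit or at unscheduled visits are not presented in the by-visit summary analyses". These values appear only in the subject listings, whatever the day of the draw.

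The protocol foresees both kinds of excluded sample. Section 5.2.11 allows any study procedure except vaccination or plasmapheresis at an unscheduled visit and adds: "Examples include repeat specimen collection and additional safety follow-up for an AE/SAE/AESI". Section 5.2.10 states: "All subjects who discontinue study participation before the Day 57 visit will be requested to undergo an Early Discontinuation/Withdrawal Visit". That visit includes "Blood collection for anti-CHIKV SNA, ELISA, PBMC".

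SAP 5.6 addresses duplicates: if there is more than one SNA sample for a time point, "the sample closest to the nominal time point is used for analysis". It does not mention unscheduled or discontinuation visits.

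Protocol 8.4 and SAP 6.5.2 rule out imputation of missing immunogenicity results, and protocol 8.4 removes a subject from any time point at which the result is missing. SAP 3.1 lists the Day 22 seroresponse rate and GMT among the primary endpoints.

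**The concern.** Whether a sample enters a by-visit summary depends on the label of the visit, not on the day the blood was drawn. Suppose a Day 22 specimen fails and is redrawn at an unscheduled visit on Day 25. The redraw is inside the Day 22 (+5) window, yet it is listed only and the subject is missing for the Day 22 endpoints. A scheduled Day 22 visit held on Day 35 would be kept.

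This fits poorly with other parts of the SAP. Section 6.5.2 intends subjects to contribute whatever data they have. Section 5.1.1 gives markedly out-of-window assessments as an example of an important deviation, yet those samples stay in while in-window ones can be left out. Under SAP 5.2, any post-injection NT80 result admits a subject to the mITT population, so a subject could qualify on a discontinuation sample that no by-visit table uses.

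At stake is avoidable loss of valid data in a study of 25, and the prospect of deciding case by case, with results in hand in an open-label study, whether a particular redraw should count.

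**Working it through.** **Inputs.** Planned N = 25 (SAP 4, set by the plasma and serum needed). Wilson 95% limits for proportions (SAP 6.1.1). 95% limits for the GMT from the mean of log10 titers (SAP 6.1.2); I take these as t-based. Windows from SAP 5.4: study Days 8–11, 13–17, 22–27 and 57–62. The plan states no power, precision or dropout figure, so there is no figure of its own to reproduce. The number of affected samples is not given either; I assume 0 to 2 per time point.

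**Can such samples fall in a window?** A discontinuation visit applies to subjects who stop before the Day 57 visit. Of study Days 2–56 (55 days), the Day 8, 15 and 22 windows cover 4 + 5 + 6 = 15 days, or 27%. The Day 22 window alone covers 6 of 55, or 11%. These are counts of calendar days, not probabilities.

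**Share of data.** One sample is 1/25 = 4%.

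**Seroresponse.** When all n subjects respond, the Wilson lower limit reduces to n/(n + z²), with z² = 1.96² = 3.84.

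| n | Calculation | Lower limit |
|---|---|---|
| 25 | 25/28.84 | 86.7% |
| 24 | 24/27.84 | 86.2% |
| 23 | 23/26.84 | 85.7% |

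**GMT.** The log-scale half-width is t(0.975, n−1) × SD/√n. The SD cancels in the ratio of n = 23 to n = 25: 0.4324/0.4128 = 1.048, so the interval is 4.8% wider. The documents give no SD for log10 titer. Over an assumed range of 0.3 to 0.6, the ratio of the upper limit to the GMT goes from 1.33 to 1.35 (SD 0.3) and from 1.77 to 1.82 (SD 0.6).

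**If the lost sample were an unusual one (illustration only).** If the single sample excluded belonged to the only non-responder, the estimate would move from 24/25 = 96.0% (80.5–99.3%) to 24/24 = 100% (86.2–100%). If 24 subjects had a GMT of 1000 and that subject a titer of 20, the GMT would move from 10^[(24×3 + 1.301)/25] = 855 to 1000. All these values are assumed.

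**Does SAP 5.6 rescue the sample?** It chooses among several samples for one time point. Where a scheduled and an unscheduled sample both exist, it does not say whether the second competes. Where the unscheduled or discontinuation sample is the only one, there is nothing to choose between and 5.4 alone applies. It also names only SNA, so ELISA and PBMC samples are not covered at all.

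**The case against.** The strongest reply is that 5.4 is a clear, prespecified convention: tables follow scheduled visits and everything else is listed. The situation should also be uncommon. The protocol's mention of repeat specimens is general and need not mean an SNA redraw. Appendix I collects 10 serum tubes at Day 22 against 2 at Days 1, 8 and 15; much of that is for nonclinical work, but losing all usable Day 22 serum is unlikely. A redraw would have to take place by Day 27. A subject who stops after the Day 22 visit already has that sample, and one who stops before Day 22 plasmapheresis may be replaced (protocol 4.3.5). A discontinuation draw inside the Day 57 window is a corner case. No hypothesis is tested.

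All of this stands as a limit on frequency and size. It does not make the exclusion of an in-window sample useful. Replacement is discretionary and adds a different subject without restoring the sample already drawn.

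A reader might infer two stronger points that the documents do not support.

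- *That SAP 5.6 contradicts 5.4.* It is silent on unscheduled and discontinuation samples. The two sections need linking, but they do not conflict outright.
- *That the loss would bias the estimates because discontinuation is selective.* Nothing in the documents links discontinuation to titer in these healthy volunteers, and protocol 1.3.3 reports 100% seroconversion by Day 57 for every regimen in the earlier Phase 2 study. The shifts illustrated above rest on assumed values.

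**Conclusion.** The point holds as a gap in the analysis rule. Followed as written, SAP 5.4 would discard valid in-window results, and nothing else in either document assigns a lone sample of this kind to a time point.

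The consequence is conditional on such samples occurring, and the documents give no expected number. If one or two are lost at a time point, the cost is 0.5 to 1 percentage point on the Wilson lower limit at 100% response, and up to 4.8% on the width of the log-scale GMT interval. No error rate or test is affected, and the values remain visible in listings. The change is worth making because it is nearly free and settles the handling before analysis, not because the primary results are in serious doubt.

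**What to change.** Keep every scheduled sample under its nominal visit, as now, and replace the exclusion sentence in SAP 5.4 with:

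> If a subject has no evaluable scheduled SNA, ELISA or PBMC result for a time point, a result from an unscheduled or early-discontinuation visit whose actual study day falls within that time point's protocol window is used; if more than one is eligible, the sample closest to the nominal day is used (Section 5.6). All other unscheduled and early-discontinuation results are listed only.

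This also settles the question left open by 5.6: an unscheduled sample fills a gap but does not compete with an evaluable scheduled one.

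Assigning every sample by actual study day would be the wrong remedy. A scheduled Day 8 draw taken late, on Day 13, would move into the Day 15 window, compete with the true Day 15 sample, and remove Day 8 data that the SAP now keeps.

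The cost is one SAP sentence and one extra programming step. No new data are needed. A discontinuation sample outside every window would still be listed only.
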